#### **BOR Based on Unconfirmed Responses**

- uCR = one CR documented before first documentation of PD
- uPR = one PR documented before first documentation of PD (and not qualifying for a CR)
- SD (applicable only to patients with measurable disease at baseline) = at least one SD assessment (or better)  $\geq 6$  weeks after date of randomization and before first documentation of PD (and not qualifying for uCR or uPR).
- Non-uCR/Non-PD (applicable only to patients with non-measurable disease at baseline) = at least one non-uCR/non-PD assessment (or better)  $\geq 6$  weeks after date of randomization and before first documentation of PD (and not qualifying for uCR or uPR).
- PD = PD after date of randomization (and not qualifying for uCR, uPR or SD).
- NE: all other cases.

An objective status of uPR or SD cannot follow one of uCR. SD can follow uPR only in the rare case that tumor increases by less than 20% from the nadir, but enough that a previously documented 30% decrease from baseline no longer holds.

**Unconfirmed Objective Response (uOR)** is defined as BOR of uCR or uPR. A patient will be considered to have achieved a uOR if the patient has a uCR or uPR which does not need to be confirmed at a subsequent assessment.

Patients who do not have a post-baseline radiographic tumor assessment or clinical evaluation due to early progression, who die, progress, or drop out for any reason prior to reaching a uCR or uPR will be counted as non-responders in the assessment of uOR. Each patient will have an objective response status (0: no uOR; 1: uOR). uOR rate (uORR) is the proportion of patients with uOR in the analysis set.

uORR by treatment arm will be calculated along with the 2-sided 95% CI using the Clopper-Pearson method (exact CI for a binomial proportion as computed by default by the FREQ procedure using the EXACT option).

In addition, the frequency (number and percentage) of patients with uBOR of uCR, uPR, SD, non-uCR/non-PD (applicable only to patients with non-measurable disease at baseline), PD and NE will be tabulated. Patients with uBOR of NE will be summarized by reason for having NE status. The following reasons will be used:

- No baseline assessment
- No post-baseline assessments due to death

- No post-baseline assessments due to other reasons
- All post-baseline assessments have overall response NE
- SD of insufficient duration (<6 weeks after date of randomization)

The association of treatment effect and uOR will be tested by the General Association Statistic of the Cochran-Mantel-Haenszel test (CMH) with the randomization strata taken into account. The null hypothesis of no association in any of the randomization strata is tested against the alternative, which specifies that there is an association between treatment effect and tumor response at least in one randomization stratum. The CMH test will be performed at 1-sided nominal alpha level of 0.025.

The stratified odds ratio in terms of uOR will also be estimated along with its 95% CI to compare study treatments. The odds ratio is defined as the odds of uOR with experimental treatment divided by the odds of uOR with control treatment. The Breslow-Day test will be used to check the homogeneity of the odds ratio across the randomization strata. It tests the null hypothesis that odds ratios in all strata are equal against the alternative hypothesis that at least in one stratum the odds ratio is different.

In case the null hypothesis of homogeneity of odds ratios across strata is not rejected at the 2-sided alpha level of 0.05, the common odds ratio will be determined using the Mantel-Haenszel estimate (by the FREQ procedure using CMH option in SAS); if the null hypothesis of homogeneity of odds ratio across all strata is rejected, the odds ratio per stratum will be calculated with the corresponding exact CI.

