### **5. GENERAL METHODOLOGY AND CONVENTIONS**

#### **5.1. Hypotheses and Decision Rules**

##### **5.1.1. Hypotheses and sample size determination**

The study is designed to test the following hypotheses:

$$H_{01}: HR_{PFS(A/B)} \geq 1, \text{ versus } H_{a1}: HR_{PFS(A/B)} < 1$$

where  $HR_{PFS(A/B)}$  represents the hazard ratio for PFS in Arm A vs Arm B.

Approximately 640 patients will be randomized to the treatment arms using a 1:1 randomization, stratified by tumor stage (<T4 vs T4), nodal stage (N0/N1/N2a/N2b vs N2c/N3), and HPV status (positive vs negative) as measured by p16 expression by IHC.

Two hundred eight-nine (289) PFS events per modified RECIST v1.1 will be required to have at least 90% power to detect a hazard ratio of 0.68 using a 1-sided log-rank test at a

significance level of 0.025, and a 2-look group-sequential design with Lan-DeMets (O’Brien-Fleming)  $\alpha$ -spending function to determine the efficacy boundary and a Gamma Family (-7)  $\beta$ -spending function to determine the non-binding futility boundary.

The sample size for this study is determined based on the assumptions that the median PFS in Arm B is 33 months (Ang KK, et al., 2010^2; Ang KK, et al., 2014) and that combination treatment with avelumab + SOC CRT (Arm A) is expected to increase the median PFS to  $\geq$  48.5 months, corresponding to a hazard ratio of 0.68 under the exponential model assumption. The sample size further assumes a 15% drop-out rate within each treatment arm and a non-uniform patient accrual over a 22-month period. The data cut-off for the primary PFS analysis will occur after the target number of events has been reached and the last patient randomized in the study has been followed for at least 24 months after randomization.

The study will also include a formal comparison for OS. The following hypotheses will be tested according to a testing strategy that preserves the overall type I error in the study as described in Section 5.1.2:

$$H_{02}: HR_{OS(A/B)} \geq 1, \text{ versus } H_{a2}: HR_{OS(A/B)} < 1$$

where  $HR_{OS(A/B)}$  represents the hazard ratio for OS in Arm A vs Arm B.

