### **6.2.2. Efficacy endpoints**

The following analyses will be based on the FAS by treatment arm unless otherwise specified.

Response endpoints (Best Overall Response [BOR], unconfirmed Objective Response [uOR], DR, TTR) will be analyzed separately based on investigator assessment per modified RECIST v1.1 and based on investigator assessment per programmatically derived standard RECIST v1.1 (Appendix 3).

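### The objective-response test is labelled 1-sided at 0.025, but the statistic and the alternative named in the SAP have no direction

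*SAP*

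**What the plan says.** SAP 6.2.2.8 (Objective response) makes three statements about one test.

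- Statistic: "The association of treatment effect and uOR will be tested by the General Association Statistic of the Cochran-Mantel-Haenszel test (CMH").
- Alternative, set against a null of no association in any stratum: "there is an association between treatment effect and tumor response at least in one randomization stratum".
- Level: "The CMH test will be performed at 1-sided nominal alpha level of 0.025".

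The same section plans an estimate: "The stratified odds ratio in terms of uOR will also be estimated along with its 95% CI to compare study treatments". Its orientation is clear: "The odds ratio is defined as the odds of uOR with experimental treatment divided by the odds of uOR with control treatment". A Breslow-Day test then checks whether the odds ratio is the same across strata. If homogeneity is rejected, a separate odds ratio with an exact interval is given for each stratum.

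No sentence says that the p-value is halved, that a signed root is used, or that the odds ratio must exceed 1 before the result counts as significant.

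**The concern.** A 1-sided test needs a statistic that distinguishes benefit from harm, or a stated rule that adds the direction. General Association for two arms and a binary outcome is a square, and the alternative written beside it admits association of either sign. Neither fits a level called 1-sided.

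Two programmers could follow this text and use different cut-offs. Under either unsigned cut-off the test can reach significance because avelumab has the lower response rate. Under the literal one, a real benefit is also tested at half the level stated. For locoregional failure and distant metastasis (SAP 6.2.2.4 and 6.2.2.5) the plan names a 1-sided stratified log-rank test at the same nominal level. A 1-sided superiority test was therefore probably intended here too, and the mismatch is particular to this endpoint.

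**Working it through.** **Inputs from the documents.** Statistic, alternative and level: SAP 6.2.2.8. Size, from SAP 5.1.1: "Approximately 640 patients will be randomized to the treatment arms using a 1:1 randomization", so 320 per arm. Three binary stratification factors give 2 × 2 × 2 = 8 strata. The analysis is on all randomized patients (SAP 6.2.2), and patients who drop out before responding count as non-responders, so the denominators stay at 320.

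**Assumptions.** Neither document gives an assumed response rate for this endpoint, or stratum shares. Control rates of 60% to 80%, the stratum shares and the spread of rates between strata are assumed below. The plan's only figure for this test is the 1-sided 0.025; it states no power.

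**1. The statistic has no sign.** For stratum k, let a be the responders in Arm A, n1 and n2 the arm sizes, m the total responders and N the total. Then

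Q = [Σ(a − n1·m/N)]² / Σ[n1·n2·m·(N − m) / (N²(N − 1))], with 1 df.

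Take two example strata with responders/non-responders of 30/10 vs 25/15 and 20/12 vs 14/18. The deviations are 30 − 27.5 = 2.5 and 20 − 17 = 3. The variances are 4.3513 and 4.0476. So Q = 5.5² / 8.3989 = 3.6017 (p = 0.0577). Exchanging the arms turns +5.5 into −5.5 and leaves Q and p unchanged.

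**2. Three readings of the level.**

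| Reading | Rejects when | Null error towards A | Null error towards B |
|---|---|---|---|
| (a) chi-square p < 0.025 | Q > 5.024 (z beyond ±2.241) | 0.0125 | 0.0125 |
| (b) chi-square p < 0.05 | Q > 3.841 (z beyond ±1.960) | 0.025 | 0.025 |
| (c) signed root of Q | z > +1.960 | 0.025 | 0 |

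Only (c) reproduces a 1-sided 0.025. A simulation with 8 strata, 320 per arm and 100,000 runs agrees. At a 70% response rate in both arms, (a) rejects 0.0122 towards A and 0.0130 towards B, (b) rejects 0.0497 in total, and (c) rejects 0.0251.

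**3. Power under (a).** For a test with 80% power at 1-sided 0.025, moving the cut-off to 2.2414 gives Φ(0.8416 + 1.9600 − 2.2414) = Φ(0.560) = 0.712. From 90% it gives Φ(1.2816 + 1.9600 − 2.2414) = Φ(1.000) = 0.841.

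With response rates, ignoring strata, for 70% vs 80%: null SE = √(2 × 0.75 × 0.25 / 320) = 0.03423 and alternative SE = √((0.21 + 0.16) / 320) = 0.03400. Power is Φ((0.10 − 1.960 × 0.03423) / 0.03400) = 0.833 at 1.960, and Φ((0.10 − 2.241 × 0.03423) / 0.03400) = 0.753 at 2.241.

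**4. Stratified simulation, share of trials called significant.**

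| Control vs avelumab | (a) | (b) | (c) |
|---|---|---|---|
| 60% vs 70% | 67.9% | 77.2% | 77.2% |
| 70% vs 80% | 76.9% | 84.7% | 84.7% |
| 80% vs 88% | 71.5% | 80.3% | 80.3% |
| 60% vs 50% (avelumab worse) | 64.0% | 73.2% | 0% |
| 70% vs 60% (avelumab worse) | 67.8% | 77.2% | 0% |
| 80% vs 70% (avelumab worse) | 76.5% | 84.4% | 0% |

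For control rates of 60% to 80% and gains of 5 to 10 points, the loss under (a) runs from about 4 points (80% vs 90%: 95.2% to 91.5%) to about 11 (60% vs 68%: 57.8% to 46.4%).

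**5. Test against interval.** The 95% interval for the odds ratio works at the 1.960 cut-off. Under (a), a z between 1.960 and 2.241 would be called non-significant beside an interval that will normally exclude 1.

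**The case against.** The best defence is that the SAP says 1-sided and an experienced programmer would act on it, by halving the p-value when the odds ratio favours avelumab or by using the signed root. Then neither the lost power nor the wrong-direction result arises. The log-rank tests for locoregional failure and distant metastasis come without such a recipe as well. This stands to the extent that the power loss is conditional. It does not remove the conflict: a named unsigned statistic and a written two-directional alternative point away from that practice, and nothing in the section settles it.

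The defence is also right about impact. The level is called nominal. SAP 5.1.2 puts only PFS and then OS in the testing sequence. Protocol 9.3.2.3 plans response rates and exact intervals by arm, with no between-arm test. The rates by arm and the odds ratio appear in the same output, so a lower response rate on avelumab could not pass for a benefit.

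A reader might go further and infer that the test is blind to opposite effects in different strata and that the alternative is therefore misstated. The documents do not support this. Breslow-Day and the stratum-specific odds ratios address heterogeneity in the same section, and low power against part of an alternative does not make that alternative wrong. Nor does the SAP say that a non-significant result would be read as no association in any stratum.

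**Conclusion.** The specification contradicts itself: an unsigned statistic and a non-directional alternative cannot deliver the 1-sided 0.025 test that is announced. The error split and the cut-offs are exact. The drop from 80% to about 71% power is plain normal arithmetic and applies only under the literal reading (a). Under (b) no power is lost, but total error is 0.05. Wrong-direction significance is possible under both. The percentages tied to response rates rest on assumed rates, stratum shares and effects.

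A reader might conclude that the trial has lost power for response, or that its error control is damaged. Neither follows. The cut-off is unresolved rather than known to be the literal one, no sample size rests on this endpoint, and the PFS and OS error rates are untouched. This is a small but real defect in the only planned between-arm hypothesis test of a secondary endpoint. It is best settled before unblinding, so that the choice is not made after the data are seen.

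**What to change.** In SAP 6.2.2.8 choose one of two consistent specifications.

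- **1-sided.** Take the signed square root of the CMH statistic, with the sign of the summed observed-minus-expected responders in Arm A. Declare significance if z > 1.960, which is the same as halving the chi-square p-value when Arm A is favoured and comparing it with 0.025. Rewrite the alternative as directional, in favour of Arm A. This matches the locoregional failure and distant metastasis tests.
- **2-sided.** Keep the General Association chi-square and its non-directional alternative, and state the level as 2-sided nominal 0.05. This matches the 95% interval for the odds ratio. Say that a significant result is read together with the direction of that odds ratio.

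The Breslow-Day step and the stratum-specific odds ratios stay as they are. The cost is two sentences of SAP text and about one line of code. No protocol change is needed on this point, because the protocol plans no between-arm response test.

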#### **3.4.2. Baseline Characteristics**

Randomization is stratified by the following, as recorded in the Interactive Response Technology (IRT):

- Tumor (T) stage (<T4 vs T4);
- Nodal (N) stage (N0/N1/N2a/N2b vs N2c/N3);
- HPV status (positive vs negative) as measured by p16 expression by IHC.

The primary analyses of PFS and OS will be stratified by these randomization stratification factors.

Other baseline characteristics (including demographics, physical measurements, and disease history) are described in Section 6.5.1. These baseline characteristics are not planned to be included as stratification variables or covariates in statistical models unless otherwise specified in Section 6.

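### If the Breslow-Day test rejects, the SAP lists no overall odds ratio for objective response, although it first promises one without condition

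*SAP*

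**What the plan says.** SAP Section 6.2.2.8 (Objective response) plans four things for the comparison of uOR between arms.

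- The response rate in each arm, with an exact 95% CI.
- A CMH test stratified by the randomization strata, at 1-sided nominal alpha 0.025. It does not depend on any other result.
- A stratified odds ratio with 95% CI. The sentence that introduces it carries no condition.
- A homogeneity check: "The Breslow-Day test will be used to check the homogeneity of the odds ratio across the randomization strata".

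The check then decides what is reported. If "homogeneity of odds ratios across strata is not rejected at the 2-sided alpha level of 0.05, the common odds ratio will be determined", by the Mantel-Haenszel method. Otherwise, "if the null hypothesis of homogeneity of odds ratio across all strata is rejected, the odds ratio per stratum will be calculated", with exact CIs. The second branch mentions no common odds ratio.

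The strata come from SAP Section 3.4.2: T stage, N stage and "HPV status (positive vs negative) as measured by p16 expression by IHC", two levels each. The introduction to SAP Section 6.2.2 has response analysed twice, per modified and per programmatically derived standard RECIST v1.1. SAP Section 6.4 plans response odds ratios with 95% CIs by subgroup, including each stratification factor, in a forest plot.

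**The concern.** The common odds ratio is the only overall between-arm effect estimate that the SAP plans for response; no risk difference is specified. A preliminary test decides whether it appears. If the test rejects, the report has a CMH p-value for the overall effect, two arm-level rates and eight stratum odds ratios, but no overall estimate with a CI that corresponds to the test. That also contradicts the unconditional sentence earlier in the same section.

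Two features make this worse. First, the rule runs separately on the two RECIST versions of response. It can fire in one and not in the other, which would set a single odds ratio beside eight stratum values with no like-for-like comparison. Second, the stratum odds ratios that take the place of the common one may be very imprecise, because eligibility thins at least one stratum.

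**Working it through.** **What the plan gives.** The documents state no power, response rate, HPV prevalence or stratum size for this test, so there is no figure of the plan's own to reproduce. They do give the size ("Approximately 640 patients will be randomized to the treatment arms using a 1:1 randomization"), the three binary factors and the 0.05 level.

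**Degrees of freedom.** 2 x 2 x 2 = 8 strata, so up to 8 - 1 = 7 df. The 5% critical value of chi-square on 7 df is 14.07.

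**Chance rejection.** With one common odds ratio in all strata, a test at 0.05 rejects in about 5% of trials. Simulation of the Breslow-Day statistic with 640 patients, 1:1, gives 4%-6%. Because the rule is applied to two RECIST versions, the chance that at least one loses its common odds ratio lies between about 5% (if they always agree) and 2 x 5% = 10% (the upper bound).

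**Power of the pre-test.** This needs inputs that the documents do not give. Assumptions: control response 50%-90%; HPV-positive share 20%-50%; T4 and N2c/N3 about 40% each; with and without a nearly empty HPV-positive/<T4/N0-N2b stratum. Each scenario had 4,000-6,000 simulated trials. Approximate share of trials in which the test does not reject, by the ratio between the HPV-specific odds ratios:

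| Ratio | Not rejected |
|---|---|
| 2-fold | 69%-94% |
| 2.5-fold | 49%-92% |
| 3-fold | 30%-92% |
| 4-fold (equal stratum mix only) | 10%-47% |

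The complement is the share of trials in which the common odds ratio is dropped: roughly 6%-31% for a 2-fold and 8%-51% for a 2.5-fold HPV difference.

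Part of the low power comes from spreading one contrast over 7 df. Where the 7-df test fails to reject 62% or 77% of the time (noncentrality 6.03 or 3.64), a 1-df HPV-by-treatment test with the same noncentrality (critical value 3.84) fails 31% or 52% of the time.

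**Precision of the replacement.** Protocol Section 4.1 admits HPV-positive oropharyngeal disease only if it is T4, N2c or N3. The HPV-positive/<T4/N0-N2b stratum can therefore hold only non-oropharyngeal tumors, and Protocol Section 1.2.3.4 says HPV-related disease is much less common at those sites. As an illustration, assume 35% HPV-positive, 4% of these in that stratum, and 70% response in both arms. The stratum then has 640 x 0.35 x 0.04 = 9 patients, or 4.5 per arm.

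Formula: SE of the log odds ratio = sqrt[2 / (n per arm x 0.7 x 0.3)]; approximate CI limits = odds ratio divided or multiplied by exp(1.96 x SE).

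| Set | n per arm | SE | CI factor |
|---|---|---|---|
| Thin stratum | 4.5 | 1.45 | 17 |
| Largest stratum (150 patients) | 75 | 0.36 | 2.0 |
| All 640 | 320 | 0.17 | 1.4 |

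The large-sample formula is itself unreliable at 9 patients. It serves only to show the order of magnitude.

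**The case against.** The best defence is that little is lost. The CMH test and the response rates by arm do not depend on Breslow-Day. Showing stratum odds ratios when heterogeneity is detected is a pre-specified and recognised convention. Objective response is secondary, tested at a nominal alpha outside the PFS-OS hierarchy of SAP Section 5.1.2, and Protocol Section 9.3.2.3 plans only rates with exact CIs by arm. No trial decision or error rate depends on this odds ratio. All of that stands, and it keeps the point minor. It does not reconcile the unconditional sentence with the branch that omits the estimate.

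Three stronger readings are tempting, and the documents do not support them.

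- *That the SAP treats a non-significant test as proof of homogeneity.* It does not say so; it only selects a summary. Failing to detect heterogeneity leads to the Mantel-Haenszel odds ratio, which is a usable weighted average and the output recommended here.
- *That an HPV difference in response would be hidden.* The forest plot in SAP Section 6.4 shows HPV-specific odds ratios whatever the test gives. What is missing is only a focused test: the interaction tests of Section 6.4 are for PFS and OS.
- *That a single miss rate belongs to this trial.* Assuming 70% control response, T4 40%, N2c/N3 45%, HPV-positive 35% and independent factors gives 77% for odds ratios of 2.0 against 1.0, and 62% for 2.5 against 1.0. The strata then range from 640 x 0.40 x 0.45 x 0.35 = 40 to 640 x 0.60 x 0.55 x 0.65 = 137 patients. None of these inputs is in the documents. Independence also puts 640 x 0.60 x 0.55 x 0.35 = 74 patients in the stratum that eligibility thins.

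**Conclusion.** The point holds for the rejection branch. As written, Section 6.2.2.8 promises a stratified odds ratio with CI and then omits the common one when Breslow-Day rejects, which leaves the CMH test without a matching overall estimate. The 5% chance loss under homogeneity follows from the SAP's own alpha. The larger losses under true heterogeneity, and the low power against a 2- to 2.5-fold HPV difference, rest on the assumed response rates, HPV share and stratum mix stated above, and should be quoted only with their ranges. That about half or more of trials would not reject at 2- to 2.5-fold holds across those ranges. The imprecision of the thinnest stratum follows in direction from eligibility, but its size is assumed. The consequence is confined to how one secondary endpoint is reported, so this is an improvement rather than a flaw in the trial's inference.

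**What to change.** Replace the conditional sentence in SAP Section 6.2.2.8 with a rule along these lines: the Mantel-Haenszel common odds ratio with its 95% CI is reported for uOR in every case, for both RECIST versions; the Breslow-Day p-value is descriptive and is shown beside the odds ratios by stratification factor already planned in Section 6.4; if it is below 0.05, the stratum odds ratios with exact CIs are shown in addition to the common odds ratio, not instead of it.

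The cost is one SAP sentence. Every quantity is already planned, so no new analysis or data are needed, and the change makes the section agree with its own opening promise. Two optional additions would help: a 1-df HPV-by-treatment test for uOR, and a pre-specified rule for pooling sparse strata.
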